The Research Design for this two-year SPIRE proposal to RR&D will comprise of testing for two cognitive-based training platforms for functional grasp and reach, respectively, on persons with cervical SCI (Fig 6A). The experimental set-ups developed at Stevens are modular and portable for conducting tests with Veterans having SCI at the James J. Peters VAMC. Testing of each platform represents a unique proposal aim. Execution of each aim will be done independently in each of the two years and similarly include: 1) adaptation of platforms for use with persons having SCI, 2) recruitment of five participants per year, 3) execution of a single 8-hour experimental session for each participant. Each session includes 3 hours for data collection, and the remaining time for preparation, rest, feeding, bathroom trips, and 90-minute washout of each experimental condition. Inclusion criteria for subjects include: 1) aged 18 to 65 years, post-SCI for more than 1 year, SCI between C1-T1 with hand weakness (2-4 out of 5 manual muscle test in intrinsic hand muscles of thumb or 5th digit).

[figure not shown]
The schedule for each 12-month aim: recruitment (months 1-6), refining protocols for SCI (months 1-6), SCI participant testing (months 6-9), data and statistical analysis (months 7-10) and dissemination via conference and paper writings and submissions (months 9-12). Recruitment will be done via IRB-approved flyers at local SCI clinics; study posting at clinicaltrials.gov; and communication with previous participants at our VAMC. Among the ten total subjects (five per aim), our enrollment plan includes at least three females, three Latinos, and three African Americans.

For each aim, the data analysis will involve *within-subject* comparisons across three conditions: (1) control with minimal-to-no cognitive feedback, (2) intermediate level of cognitive feedback, and (3) enhanced cognitive feedback. Enhanced feedback refers to addition of VR to glove feedback in Aim 1, and addition of vibration to visual feedback in Aim 2. For each condition, there will be three consecutive trial blocks (Fig 6B): 1) baseline – performing real-world task 25 times with no feedback before training, 2) training – performing training task 50 times with feedback specific to condition, 3) retention – performing real-world task 25 times with no feedback after training.

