Repeated-measures MANOVA will be utilized given the three condition groups and two or more performance metrics specific to each aim. Our previous analyses for Result #1 with able-bodied persons suggest that $n = 5$ is sufficient to show significant difference ($p < 0.05$) for MANOVA across three condition groups and two performance metrics (completion time, motion pathlength) at 90% power. **The primary hypothesis for each aim is that performance after training is significantly greater with enhanced feedback.** Both aims of this study will also capture 32-channel EEG recordings for exploratory analysis of coherence computations with select recordings of muscle EMG as in Fig 2C.

AIM 1: Investigate the effect of a “cognition” glove and virtual reality on grasp performance in SCI persons with partial hand paralysis.

The cognition glove protocol from Result #1 will be extended to include VR feedback to persons with SCI performing the grasp-and-place of a small cubic object.

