Challenges/Alternatives – There are two primary challenges to this project: 1) *For Aim 1, the ability of a person with SCI and compromised sensation to find and skillfully grasp the real object while viewing the virtual environment.* If the subject is overly challenged to grasp the real object, then virtual feedback will be provided in desktop mode. VR goggles will be removed, and the participant can see and grasp the real object directly while a virtual environment is projected onto a background monitor. We expect viewing the virtual environment peripherally will still have additive reinforcement effects [53]. 2) *For Aim 2, subjects with various levels of SCI and conditioning may experience more fatigue than others given a total of 300 trials per session.* For each Aim, condition 1 allows us to re-calibrate our procedures based on participant behavior and apparent onset of fatigue. Re-calibration includes longer rest periods and fewer trials. A pilot analysis in persons without SCI for a reach-to-touch task done in our lab [54] suggests MANOVA significant differences in performance (pathlength and contact accuracy) across two feedback conditions (reward, punishment) could be observed with only 40 trials per condition. For both Aims, fatigue will also be monitored from EMG recordings [55].

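### The re-calibration rule implies that the no-feedback control runs first; if so, enhanced versus control on the post-training score is confounded with position in the session

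*Combined protocol and SAP*

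**What the plan says.** Section (c), Research Design and Methods, sets a within-subject comparison of three conditions in one 8-hour session, with five participants per aim.

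- **Condition 1** is "control with minimal-to-no cognitive feedback". The Aim 1 and Aim 2 protocols also list the no-feedback condition first.
- **Blocks.** Each condition has a baseline block ("performing real-world task 25 times with no feedback before training"), 50 training trials and 25 retention trials. The session also provides for "90-minute washout of each experimental condition".
- **Re-calibration.** Challenges/Alternatives names fatigue as a main challenge, "given a total of 300 trials per session". It then says: "For each Aim, condition 1 allows us to re-calibrate our procedures based on participant behavior and apparent onset of fatigue". And: "Re-calibration includes longer rest periods and fewer trials".
- **Analysis.** "Repeated-measures MANOVA will be utilized given the three condition groups and two or more performance metrics specific to each aim". The primary hypothesis of each aim concerns performance after training. How the baseline block enters the analysis is not stated.

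No sentence gives the order of the conditions, a randomised or counterbalanced sequence, or a period term. Section (c) cites Fig 6 for the design and the trial blocks, and that figure is not available here.

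**The concern.** Condition 1 can inform the rest and trial numbers of the other conditions only if it comes before them. Read with the numbering, that puts control first for all five participants in each aim. The enhanced-versus-control comparison would then also compare a later part of a long session with its start.

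Two things differ along that line besides feedback. One is accumulated practice and fatigue. The other, if re-calibration is used, is the rest and number of trials themselves, since control would be run under the initial schedule and the feedback conditions under the revised one.

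Superiority of enhanced feedback is the primary hypothesis of both aims, and the training approaches are to be carried into the later award.

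**Working it through.** **1. The plan's own count.** 3 conditions × (25 + 50 + 25) = 300 trials per session, as stated.

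**2. Can condition be separated from position on the post-training score?** Take one score per participant and condition: 5 × 3 = 15 rows. The model has 5 participant, 2 condition and 2 period columns, 9 in all.

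| Order | Rank | Enhanced − control estimable? |
|---|---|---|
| 1-2-3 for all | 7 of 9 | no |
| Control first, 2 and 3 alternated | 8 of 9 | no (only 3 versus 2) |
| Any five of the six orders | 9 of 9 | yes, variance 0.417σ² |

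This needs no assumption about the size of any drift.

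**3. What do the planned baselines add?** Put the 15 baseline scores in as well, under the order 1-2-3. With participant (5), period (2), phase (1) and phase-by-condition (2) terms, the rank is 10 of 10. The enhanced-minus-control change is therefore estimable, provided that period shifts baseline and retention equally. If the baseline-to-retention change may itself depend on position (two phase-by-period columns more), the rank stays at 10, now of 12, and the contrast is lost again.

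**4. Size, for the unadjusted post-training score.** Assume no feedback effect, one shared order and a linear drift of d residual SD per period. For one metric the repeated-measures test is F(2, 8), with noncentrality λ = 5 × (1 + 0 + 1) × d² = 10d². The MANOVA column assumes two metrics, participant blocks, Wilks' test, correlation 0.5 and drift in both metrics.

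| d (assumed) | λ | False rejection, univariate | Two-metric MANOVA | Change score, additive drift |
|---|---|---|---|---|
| 0.25 | 0.625 | 8% | 8% | 5% |
| 0.5 | 2.5 | 20% | 17% | 5% |
| 1.0 | 10 | 64% | 56% | 5% |

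With control first and conditions 2 and 3 randomised independently, the univariate rates are 8%, 15% and 43%. With five of the six orders and a period term they are 5% throughout.

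**5. Direction.** On the post-training score, retained practice favours enhanced and fatigue works against it. On the change score the effect of practice reverses. Assume a power-law practice curve with exponent 0.1, and that a quarter of earlier trials still count after the washout. Practice alone then improves the score from baseline to retention as follows:

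| Trials counted | First position | Second | Third |
|---|---|---|---|
| All | 19.7% | 10.5% | 7.6% |
| Real-task only | 12.5% | 6.9% | 5.1% |

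With no retention the three positions are equal. With this pattern, practice could hide a true benefit on the change score but could not create one.

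**The case against.** **The order is not stated.** Control-first is an inference, Fig 6 may show a varied order, and condition 1 could mean whichever condition is run first, though the numbering makes that less likely. This stands. A reader might infer that the plan fixes control first; it does not say so, and the finding is conditional on it.

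**The contrast can be recovered.** Each condition has its own baseline, and a washout is planned. A reader might infer from the rank check that no analysis could separate feedback from position. That holds only for the post-training score, or where the change itself depends on position (steps 2 and 3). The washout reduces carry-over, but nothing in the plan shows that it is complete.

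**The endpoint is inconsistent.** A reader might take the Aim 1 remark on improvement from baseline as contradicting the primary hypothesis. It describes the earlier able-bodied study and does not define this trial's endpoint. What stands is that the role of the baseline block is unstated.

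**Control-first protects control from feedback carry-over.** This is a real trade-off. Assume that condition 2 has half the enhanced effect and that carry-over comes only from the preceding condition. With five of the six orders and a period term, the enhanced-minus-control estimate falls to 90%–93% of truth at 25% carry-over and to 58%–71% at full carry-over. The fixed order is distorted too, in the other direction: 1 + 0.5 × 0.25 = 113% of truth at 25%, and 1 + 0.5 × 1 = 150% at full carry-over.

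**Conclusion.** The concern holds in conditional form. If control runs first for everyone, as the re-calibration rule implies, enhanced versus control on the post-training score is confounded with position in the session, and possibly with unequal trials and rest. Analysing change from each condition's own baseline removes a shift common to baseline and retention, but not position-dependent learning or fatigue.

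The confounding follows from the order alone; its size does not. The 8%, 20% and 64% rest on assumed drifts, one shared order and an unadjusted post-training score. The true bias could be near zero. A reader might infer that the bias favours enhanced feedback; the documents do not support a direction, since practice and fatigue oppose each other and the effect of practice reverses on a change score.

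This should be fixed before testing starts. Confidence is medium, because the order is inferred.

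**What to change.** 1. **Order.** Randomise the order of the three conditions per participant, for example five of the six sequences drawn without replacement in each aim. If Fig 6 already gives a varied order, state it in the text and reconcile the re-calibration rule with it.
2. **Endpoint.** State whether it is the post-training score or baseline-adjusted change, and show the three baseline blocks by period.
3. **Re-calibration.** Reconcile it with the chosen order, for instance by basing it on calibration already planned before the conditions (the glove calibration in Preliminary Studies, the EMG classifier data in Aim 2). Plan equal trial counts and rest across conditions within a participant, keep the accommodation for fatigue available, and record departures by condition.
4. **Analysis.** Include a period term, at least as a sensitivity analysis.
5. **If control must stay first,** randomise conditions 2 and 3 and report enhanced versus control as descriptive.

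**Cost.** The order itself needs only a randomisation list. The period term widens the univariate interval by about 8%: √(0.417/0.400) × t(6)/t(8) = 1.021 × 1.061 = 1.083. In the two-metric MANOVA (correlation 0.5), an effect detected with about 90% power has about 78% with the term. Five participants cannot balance six orders, and the carry-over risk to a later control block remains.

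A separate 25-trial familiarisation run would take about 15 minutes (3 hours / 300 trials = 36 s each) and might miss late fatigue. Time is tight: 3 hours of data plus two or three 90-minute washouts use 6.0 or 7.5 of the 8 hours. Existing calibration is therefore the cheaper basis.
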